## **List of abbreviations:**

AE	Adverse Event
AUC	Area under the curve
CA	Competent Authority
CADT	Centre for Affordable Diagnostics and Therapeutics
CI	Chief Investigator
CIC	Clinical Investigation Centre
Chk1/Chk2	Checkpoint kinase 1/Checkpoint kinase 2
Cip/Kip	CDK interacting protein/Kinase inhibitory protein
CD31	Cluster of Differentiation 31
CRF	Case Report Form
CT	Computed tomography
CTA	Clinical Trial Authorisation
CTCAE	Common Terminology Criteria for Adverse Events
CTC	Common Toxicity Criteria
CTIL	Clinical Trial Import License
DHA	Dihydroartemisinin
DNA	Deoxyribonucleic acid
DDSB	DNA double-strand breaks
DMC	Data Monitoring Committee
DSUR	Development Safety Update Report
EGFR	Epidermal Growth Factor Receptor
eGFR	Estimated Glomerular Filtration Rate
EORTC	European Organisation for Research and Treatment of Cancer
GCP	Good Clinical Practice
GCSF	Granulocyte colony-stimulating factor
GFR	Glomerular Filtration Rate
GMP	Good Manufacturing Practice
g/l	grams per litre
Hb	Haemoglobin
HIF-1 $\alpha$	Hypoxia induced factor - 1 $\alpha$
HPV	Human Papilloma Virus
IB	Investigator Brochure
ICF	Informed Consent Form
ID	Identification
IMP	Investigational Medicinal Product
IIT	Investigator Initiated Trial
IP	Intellectual Property
ISF	Investigator Site File
ISRCTN	International Standard Randomised Controlled Trial Number

ITT	Intention to treat
KG	Kilogram
LFT	Liver Function Test
MG	Miligram
ML	Mililitre
MMPs	Metalloproteinases
MOH	Ministry of Health
NCAM	Neural cell adhesion molecule
NF- $\kappa$ B	Nuclear factor kappa-light-chain-enhancer of activated B cells
NMRR	National Medical Research Register
NPRA	National Pharmaceutical Regulatory Agency
NoK	Next of Kin
OD	Once daily
PBMC	Peripheral blood mononuclear cell
PI	Principal Investigator
PIS	Participant Information Sheet
Plts	Platelets
PO	Oral administration
QC	Quality Control
QOL	Quality of Life
QP	Qualified Person
R&D	Research & Development
REC	Research Ethics Committee
ROS	Reactive Oxygen Species
RSI	Reference Safety Information
SAR	Serious Adverse Reaction
SAE	Serious Adverse Event
SDV	Source Document Verification
SmPC	Summary of Product Characteristics
SOP	Standard Operating Procedure
SSAR	Suspected Serious Adverse Reaction
SUSAR	Suspected Unexpected Serious Adverse Reaction
TF	Transferrin
TIMP	Tissue inhibitors of metalloproteinase
TMF	Trial Master File
TMG	Trial Management Group
TSC	Trial Steering Committee
TPP	Time to progression
ULN	Upper limit of normal
UM	University of Malaya
UMMC	University Malaya Medical Centre
VEGF	Vascular endothelial growth factor
WCC	White Cell Count
WHO	World Health Organisation

## Protocol Summary

[figure not shown]
Trial number and full title	Phase II Single Arm, Open Label Study of Artesunate for the Treatment of Human Papilloma Virus positive High Grade Cervical Intraepithelial Neoplasia (CIN2/3)														
Protocol number	2023-MHL-002														
Rationale	
Artesunate belongs to the artemisinin family of sesquiterpene trioxane anti-malarial agents derived from Sweet wormwood (Artemisia annua L.) that have been used in traditional Chinese medicine for centuries to treat a variety of ailments including fever, inflammation and haemorrhage. Artesunate is approved for the treatment of uncomplicated, severe and multidrug-resistant malaria, is on the WHO list of Essential Medicines with an excellent safety profile and is affordable at USD1 per daily dose.
 
Several comprehensive reviews have examined the evidence for the anti-cancer effects of artemisinins. Pre-clinical studies of artemisinins in cell line and animal models have demonstrated broad anti-cancer activity including pro-apoptotic, anti-proliferative, anti-angiogenesis and anti-metastatic effects. A Phase I dose-escalation study of artesunate vaginal inserts in biopsy-confirmed CIN 2/3 in 28 patients showed that treatment was safe and well tolerated with histologic regression observed in 19/28 (67.9%) subjects and HPV viral clearance in 9/19 subjects (47.4%) (Trimble et al., 2020). In patients who did not experience histological regression, no viral clearance was seen.
 
NeoART-CIN is a Phase II clinical study evaluating the safety and effectiveness of oral artesunate in patients with CIN2/3, to investigate if a course of treatment with oral artesunate can lead to regression of pre-cancerous changes in the cervix and prevent the development and progression of invasive cancer. Findings from this study will increase our understanding of the effects of artesunate on CIN2/3 and, if confirmatory, inform future clinical studies.
														
Objective(s) + Endpoint(s)	
Overall objective: To determine the feasibility, safety and preliminary anti-proliferation activity of oral artesunate in Human Papilloma Virus positive (HPV +ve) High Grade Cervical Intraepithelial Neoplasia (CIN2/3).
 
 
 Primary Objective	Primary Endpoints	
 
 To determine the effect of artesunate on histologic regression of CIN2/3	Histological regression of CIN2/3 on colposcopy and biopsy at Day 90	
 
 Secondary Objective	Secondary Endpoints	
 
 To determine the effect of artesunate on HPV DNA viral clearance	HPV DNA viral clearance at Day 90	
 
 To determine the effect of artesunate on the vaginome and gut microbiome	Comparison of vaginome and gut microbiome at Day 0, Day 64 and Day 90	
 
 To determine the effects of artesunate on patient safety	Serious Adverse Event at 90 days using Common Toxicity Criteria (CTCAE V5.0)	
 
 To determine the effects of artesunate on patient Quality of Life	Quality of life using the European Quality of Life-5 Dimensions (EQ-5D) quality of life tool	
 
	Primary Objective	Primary Endpoints	To determine the effect of artesunate on histologic regression of CIN2/3	Histological regression of CIN2/3 on colposcopy and biopsy at Day 90	Secondary Objective	Secondary Endpoints	To determine the effect of artesunate on HPV DNA viral clearance	HPV DNA viral clearance at Day 90	To determine the effect of artesunate on the vaginome and gut microbiome	Comparison of vaginome and gut microbiome at Day 0, Day 64 and Day 90	To determine the effects of artesunate on patient safety	Serious Adverse Event at 90 days using Common Toxicity Criteria (CTCAE V5.0)	To determine the effects of artesunate on patient Quality of Life	Quality of life using the European Quality of Life-5 Dimensions (EQ-5D) quality of life tool
Primary Objective	Primary Endpoints														
To determine the effect of artesunate on histologic regression of CIN2/3	Histological regression of CIN2/3 on colposcopy and biopsy at Day 90														
Secondary Objective	Secondary Endpoints														
To determine the effect of artesunate on HPV DNA viral clearance	HPV DNA viral clearance at Day 90														
To determine the effect of artesunate on the vaginome and gut microbiome	Comparison of vaginome and gut microbiome at Day 0, Day 64 and Day 90														
To determine the effects of artesunate on patient safety	Serious Adverse Event at 90 days using Common Toxicity Criteria (CTCAE V5.0)														
To determine the effects of artesunate on patient Quality of Life	Quality of life using the European Quality of Life-5 Dimensions (EQ-5D) quality of life tool														
Study design	Phase II open label single arm study														

Number of patients (statistical design)	A maximum of 28 participants will be enrolled to receive the study intervention. The primary end point is histological regression of CIN2/3 on colposcopy and biopsy at Day 90. Significance level and power: The procedure described above tests the null hypothesis that the response rate is 20 % versus alternating hypotheses that the response rate is 50 %. The significance level (i.e., the probability of rejecting H0 when it is true) is $\alpha=0.1$ and the power (i.e., 1-beta, the probability of deciding the regimen is active) is 90% when true response rate is 50 %. At the significance level of 0.05, with an equivalence limit of 0.15, a sample size of 24 is required to achieve 90% power when the response rate for the historical control is 0.2 and response rate for the treatment is 0.5. Inflating this sample size by 20% to allow for loss at follow-up would result in a sample size of approximately 28 patients.
Trial population	
Main inclusion criteria
 
 
• Aged 18 or over
 
• Histologically proven HPV positive cervical CIN2/3
 
• WHO performance status 0-2
 
• Adequate full blood count: 
 
◦ White Cell Count (WCC) <math>>3.0 \times 10^9 /l</math>;
 
◦ Platelets <math>>100 \times 10^9 /l</math>;
 
◦ Haemoglobin (Hb) <math>>80g/L</math>
 
 
 
• Adequate renal function: 
 
◦ Glomerular Filtration Rate <math>>30ml/min</math>
 
 
 
• Adequate hepatobiliary function: 
 
◦ Total bilirubin <math>< 3 \times</math> Upper limit normal
 
 
 
• Participants of child bearing potential must have a negative pregnancy test <math>< 72</math> hours prior to initiating study intervention and agree to avoid pregnancy using adequate, medically approved contraceptive precautions for up to 6 weeks after the last dose of study treatment intervention
 
• Patient able and willing to provide written, informed consent for the study
 
 
Main exclusion criteria
 
 
• Contraindication to the use of artesunate due to hypersensitivity
 
• Pregnancy or lactation
 
• Weight <math>< 52</math> kg
 
• History of previous CIN
 
• Immunocompromised patients
 

Treatment	
Study Intervention:
 
Patients with HPV positive CIN2/3 will receive 3 cycles of oral artesunate 200mg OD prior to standard of care therapeutic large loop excision of transformation zone (LLETZ). Each 21 day treatment cycle will comprise oral artesunate 200mg OD for 14 days followed by a 7 day treatment break.

Reference Treatment	Not applicable.
Statistical analyses	Patients' demographics, baseline characteristics, prior and concomitant medications, treatment exposure, protocol compliance and study withdrawals will be summarized in the intent-to-treat population. For categorical variables, frequency tables (with %) will be presented with descriptive listings of details specified in text fields, where appropriate.

	
Continuous variables will be reported using median, range and interquartile range.
 
Primary outcome measure(s)
 
 
• Histological regression of CIN2/3 on colposcopy and biopsy at Day 90 will be defined as histologic regression to CIN1 or less. This will be described as a response percentage.
 
 
Secondary outcome measure (s)
 
 
• HPV DNA viral clearance at Day 90 Viral clearance will be defined as absence of HPV genotype(s) that were detected at baseline and described as a response percentage.
 
• Vaginome and gut microbiome at Day 1, Day64 and Day 90 Changes in vaginome and gut microbiome will be compared between Day 0, Day 64 and Day 90.
 
• Serious Adverse Events at Day 90 using Common Toxicity Criteria (CTCAE V5.0) Safety assessment will be based on patients who received at least one dose of IMP. Tolerability assessment will be based on the percentage of subjects that complete the designated dosing regimen.
 
• Patient quality of life will analysed using the European Quality of Life–5 Dimensions (EQ-5D) quality of life analysis tool.
 

Translational research	
Study Assessments:
 
Patients will have study bloods samples for translational research collected on Day 1, Day 14, Day 64 and Day 90 of the study. HPV DNA will be tested on vaginal sampling Day 1, Day 64 and Day 90 of the study. Vaginome and microbiome samples will be collected on Day 1, Day 64 and Day 90. A laboratory manual has been prepared separate to this protocol.

Quality of Life	European Quality of Life–5 Dimensions (EQ-5D-5L) quality of life tool will be completed on Day 1, Day 7, Day 14, Day 22, Day 43, Day 64 and Day 90 of the study.
Benefit-risk analysis	Cervical cancer represents significant morbidity and mortality globally, particularly in Low and Middle Income Countries (LMICs). The current standard of care in women with pre-cancerous high grade CIN2/3 are surgical or ablative treatments. Although these treatments are generally safe, there remains a small risk of complications such as infection, bleeding, perforation, and cervical stenosis with the most severe late complication being an increased risk of preterm birth and obstetric complications. Following surgical resection, the risk of recurrence with uninvolved margins may range from 8-23% ((Nagai et al. , 2000 ; Serati et al. , 2012 ; Fan et al. , 2018 ; Verguts et al. , 2006)). For many women, travel costs, time off work and childcare considerations represent significant barriers to engaging with cervical cancer screening, treatment and follow up. There is an urgent need to develop affordable therapeutics at point-of-need to manage the burden of global oncology. A safe, effective, affordable and convenient oral treatment that results in regression of CIN2/3 and clears HPV infection would represent a significant development in the management of this condition.

Trial-specific risks and burdens include additional diagnostic, therapeutic and monitoring procedures to ensure safety, tolerability and preliminary antiproliferative effects in this patient population. Patients may not derive any direct benefit from participating in this study. However they will contribute to our scientific and clinical understanding of the potential antiproliferative effects of artesunate in CIN2/3 as we research better treatments for this condition.

**Phase II single arm open label study of oral artesunate in Human Papilloma Virus positive High Grade Cervical Intraepithelial Neoplasia (CIN2/3)**

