## 2.2 Background Therapeutic Information

Artesunate is derived from a plant called Sweet Wormwood (*Artemisia annua* L. / 'Qing Hao'), which has been used for more than two thousand years in traditional Chinese medicine to treat a variety of ailments (Augustin *et al.*, 2020 ; Krishna *et al.*, 2008). Pre-clinical studies of artemisinins in cell line and animal models have demonstrated broad anti-cancer activity including pro-apoptotic, anti-proliferative, anti-angiogenesis and anti-metastatic effects (Augustin *et al.*, 2020; Krishna *et al.*, 2014 ; Ho *et al.*, 2014).

[figure not shown]
Artesunate, artemether and arteether are derivatives of artemisinin that are converted into their active metabolite dihydroartemisinin (DHA). Artesunate is approved for the treatment of uncomplicated and multidrug-resistant malaria and is on the WHO list of Essential Medicines (WHO., 2015). Artesunate has a hemisuccinate group which confers substantial water-solubility and high oral bioavailability and therefore a convenient oral route of administration. Artesunate has a good safety and tolerability profile, having been used to treat tens of millions of adults and children globally (Hien *et al.*, 1994 ; Kremsner *et al.*, 2004).

The dose of artesunate for the study will be 200 mg per oral (PO) once daily (OD) for fourteen days per treatment cycle. There are no data on the most appropriate dose of artesunate in cancer in humans. This dose has been chosen by a consensus among medical experts experienced with using artesunate for the treatment of malaria and following published results from a pilot feasibility and

safety study of neodajuvant oral artesunate in patients with colorectal cancer (Krishna *et al.* 2015).

The daily dose of artesunate used in combination treatments to treat uncomplicated *Plasmodium falciparum* malaria is 4 mg/kg, given over three days. When given as monotherapy for uncomplicated falciparum malaria the total dose is approximately 20 mg/kg, over seven to ten days. For curative courses in severe malaria, the total doses of artesunate (parenteral and oral combined) can reach 24 mg/kg. The daily dose of artesunate for a patient in this study will be between 2 mg/kg and 4 mg/kg, depending on the weight of the participant (ranging between 52-110 kg). At daily doses of 6 mg/kg the dose limiting side effect of artesunate is neutropenia.

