### **4. Patient Selection Criteria**

There will be no exceptions (waivers) to eligibility criteria prior to participant inclusion into the study. Any questions raised about eligibility should be addressed prior to entering the participant.

The eligibility criteria have been carefully considered and are standard to ensure both the safety of the participants and that the trial results can be appropriately used to make future treatment decisions for other patients with similar disease or medical condition. It is therefore vital exceptions are not made to the following detailed selection criteria.

Deviations from the eligibility criteria are considered to be protocol violations and may be reported to the NPRA as a serious breach.

All participants that are screened for inclusion into the study must be entered onto the Sponsor screening log and will be assigned a sequential number. Participants will be considered eligible for enrolment into this trial if they fulfil all of the inclusion criteria and none of the exclusion criteria as defined below.

Eligible participants will be entered onto the Sponsors Subject ID log and assigned a Trial specific Identification number in a pre-agreed format in accordance with Site identifier and next sequential numerical value e.g. PPUM001.

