## 4.2 Exclusion criteria

- Contraindication to the use of artesunate due to hypersensitivity
- Pregnancy or lactation
- Weight < 52 kg
- History of previous CIN
- Immunocompromised patients

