### **5.1.5 Dose and schedule modifications**

No dosage modifications will be undertaken. Any Grade 3/4 reaction (according to Common Terminology Criteria for Adverse Events (CTCAE) Version 5.0) which occurs in any patient and is deemed related to the IMP by the treating investigator will result in that patient's trial treatment being discontinued. If patients develop Grade 3 neutropenia or more (according to the Common Terminology Criteria for Adverse Events (CTCAE) Version 5.0) they should be managed with granulocyte colony stimulating factor (GCSF) supplied via routine hospital pharmacy in accordance with local policy and prescribing practice. The study drug will be stopped and they will continue to be monitored until their full blood count recovers. They will not be recommenced on the study drug but will continue to be followed up within the trial.

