### **5.3 Withdrawal criteria**

Patients may discontinue study treatment or withdraw their consent to participate in the study at any time without prejudice. In consenting to the trial, participants are consenting to trial treatments, trial follow up and data collection. However, an individual participant may stop treatment early or be stopped early for any one of the following reasons :

- Unacceptable treatment toxicity or an adverse event
- Investigator decides that it is in the best interests of the patient to terminate his/her participation in the study
- Poor patient compliance and/or major protocol deviation
- Intercurrent illness that prevents further protocol treatment

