### D1 of study

- Baseline safety blood tests full blood count (FBC), Urea and Elelctrolytes (U&E), Liver Function Tests (LFTs) will be conducted at D1
- Baseline study blood tests (plasma, Peripheral Blood Mononuclear Cell (PBMC)) will be collected at D1
- Vaginome and gut microbiome samples will be collected at D1
- Quality of Life Tool (European Quality of Life-5 Dimensions (EQ-5D))

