## 9. Data Collection Tool

All data will be handled in accordance with the Data Protection Act. The Case Report Forms (CRFs) will not bear the participant's name or other directly identifiable data. The participant's trial Identification Number (ID) only will be used for identification. The Sponsor Subject ID log can be used to cross reference participant's identifiable information.

Case Report Forms will be designed by the CI and the CI delegate and the final version will be approved by the Sponsor.

It is the Investigator's responsibility to ensure the The Staff Delegation of Responsibilities Log is completed and all data entered and recorded in the CRFs are accurate. The Staff Delegation of Responsibilities Log will identify all trial personnel responsible for data collection, entry, handling and managing the trial Redcap database. Basic demographic and clinical information will be gathered at the time of the initial interview and by review of the medical notes if needed.

All laboratory analysis should be reviewed by the PI and where results reported are not within the normal range the PI must clearly annotate 'Not clinically Significant' or 'Clinically significant' and sign and date the results. The relevant results should be carefully transcribed to the Case Report Forms.

In order to ensure completeness of data collected, participants will be contacted by the research team (telephone call/letter) in the event of missing data such as patient quality of life questionnaires.

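### The entry blood count sets no neutrophil minimum, although grade 3 neutropenia permanently stops the drug, so a patient can qualify just above the stop level

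*Protocol*

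**What the plan says.** **Entry.** The Protocol Summary and Section 4.1 give the same three blood-count limits: total white cells ("White Cell Count (WCC") above 3.0 ×10⁹/l, platelets above 100 ×10⁹/l and haemoglobin above 80 g/L. Neither place mentions neutrophils. The nearest exclusion in Section 4.2 is "Immunocompromised patients", which is not defined. Section 4 lets the written lists decide entry: "Participants will be considered eligible for enrolment into this trial if they fulfil all of the inclusion criteria and none of the exclusion criteria". It allows no waivers.

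**Stopping.** Section 5.1.5 stops the drug at grade 3 neutropenia or more under CTCAE v5.0, and the stop is permanent: "They will not be recommenced on the study drug but will continue to be followed up within the trial".

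**Known toxicity.** Section 2.2 states: "At daily doses of 6 mg/kg the dose limiting side effect of artesunate is neutropenia". Section 7.2, as its table reads, places neutropenia in the uncommon category.

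**Checks around the first dose.** The Day 1 procedures include "Baseline safety blood tests full blood count (FBC"), and Section 6.4 places the Day 1 review before medication starts. Section 9 requires that "where results reported are not within the normal range the PI must clearly annotate" whether the result is clinically significant. Section 5.3 allows treatment to be stopped when the "Investigator decides that it is in the best interests of the patient to terminate his/her participation in the study". None of these gives a neutrophil value.

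**The concern.** The entry rule and the stop rule use different measures. Entry looks at total white cells; stopping looks at neutrophils, the one cell type for which the Protocol names a dose-limiting effect and provides its own stop rule. A woman with little neutrophil reserve can therefore meet every listed criterion. Whether she starts depends on the investigator's judgement and not on a stated count.

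The main stake is safety. These women have a pre-malignant condition with an established treatment, and the benefit-risk section of the synopsis accepts that they may gain nothing directly. An avoidable grade 3 neutropenia would bring G-CSF and permanent loss of study treatment.

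Interpretation is a smaller matter. A woman stopped this way counts as not completing the regimen, the tolerability measure in Section 10.2.4, and adds to the grade 3–4 toxicity proportion. Part of that result would reflect her count at entry and not the drug alone.

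**Working it through.** The plan gives no figure on this point to reproduce. The check compares the two rules and then works out how close to the stop level an eligible patient can be.

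**Inputs**
- Entry: white cells > 3.0 ×10⁹/l (Protocol Summary; Section 4.1).
- Stop: grade 3 neutropenia, CTCAE v5.0 (Section 5.1.5). The numeric limit L is not printed in the Protocol text. *Assumption:* L = 1.0 ×10⁹/l, with a range of 0.5 to 1.5.
- Illustrative patient: white cells 3.1 ×10⁹/l, 35% neutrophils. This is a chosen example; the Protocol gives no frequency for such counts.
- Dose 200 mg daily; weight 52 to 110 kg (Section 2.2). Sample size 28 (Section 10.1).
- Uncommon means at least 1/1000 and below 1/100 (Section 7.2).

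**Formulas**
- Neutrophil count = white cells × neutrophil share.
- Share at which the count equals the limit = L / white cells.
- Fall that reaches the limit = 1 − L / count.

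**Distance from the stop level.** The example patient has 3.1 × 0.35 = 1.085 ×10⁹/l.

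| Assumed L (×10⁹/l) | Share equal to L at white cells 3.1 | Fall from 1.085 to L | Entry minimum 1.5 × L | Fall from that minimum to L |
|---|---|---|---|---|
| 0.5 | 0.5/3.1 = 16% | 1 − 0.5/1.085 = 54% | 0.75 | 33% |
| 1.0 | 1.0/3.1 = 32% | 1 − 1.0/1.085 = 8% | 1.5 | 33% |
| 1.5 | 1.5/3.1 = 48% | already below L | 2.25 | 33% |

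The last column is 1 − 1/1.5 = 33% whatever L is. With L = 1.0 and a 30% share, the count is 3.1 × 0.30 = 0.93, so the written criteria would admit a woman already below the stop level. For any L below 3.0, the white cell rule alone cannot prevent this.

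**Dose.** 200/52 = 3.85 mg/kg and 200/110 = 1.82 mg/kg. These are 3.85/6 = 64% and 1.82/6 = 30% of the 6 mg/kg daily dose.

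**Expected number.** 28 × 0.001 = 0.03 to 28 × 0.01 = 0.28 neutropenia cases of any grade. Only some of these would start with low counts.

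**Effect on tolerability.** Each patient stopped costs 1/28 = 3.6 percentage points.

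**When a minimum would act.** Sections 6.2 and 6.4 schedule a blood count on the first day of each course (Days 1, 22 and 43). After Day 1 the next is on Day 14, the last dosing day of course 1. Day 1 is therefore the point at which an entry minimum would protect.

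**The case against.** The two rules do not contradict each other: one governs entry, the other acts on treatment, and the Protocol does set a white cell floor. How close an eligible patient stands to the stop level depends on a limit the Protocol text does not print; at 0.5 the example patient would need a 54% fall. The example itself is hand-picked.

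There are also safeguards. The white cell criterion already requires a blood count to be seen before dosing, and an abnormal result must be annotated. After entry there are a Day 7 telephone toxicity check and diary card (Section 6.4), a 24-hour emergency card (Section 5.3), G-CSF and monitoring until recovery (Section 5.1.5), and tolerability reviews after 3 and 14 patients (Section 10.1.1). Finally, a woman stopped for neutropenia truly did not complete the regimen, so the tolerability percentage is not biased; a minimum changes who is studied.

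Most of this stands, and it limits the weight of the point. It does not remove it. The later safeguards act after exposure, and none of the earlier ones states a neutrophil count below which treatment should not begin. The low expected number is also uncertain in either direction. Section 5.1.8 puts malaria treatment at 3–5 days on average, against three 14-day courses here, and Section 7.2 says its frequencies rest mostly on published post-approval data, not adequately sized trials.

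**Conclusion.** The point holds as a minor, cheap safety improvement. The eligibility text lacks a neutrophil minimum, and total white cells above 3.0 ×10⁹/l does not keep a patient clear of a permanent stop rule based on neutrophils. Under an assumed grade 3 limit of 1.0 ×10⁹/l, an eligible woman can be 8% above the stop level, or already below it.

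The existence of the gap does not depend on that assumption, provided the limit is below 3.0; the size of the margin does. Few of the 28 patients are likely to be affected, and how many would enter with low neutrophils cannot be estimated from the Protocol. The primary endpoint, power and sample size are untouched. Eligibility is fixed in the protocol, so this is not a detail that a statistical analysis plan would supply.

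**What to change.** Add one line to Section 4.1 and one to the synopsis: an absolute neutrophil minimum clearly above the CTCAE v5.0 grade 3 limit, checked on the Day 1 blood count before the first dose. A minimum of 1.5 times the limit (≥1.5 ×10⁹/l if the limit is 1.0) leaves room for a fall of at least 33%. The multiple of 1.5 is a suggestion and has no source in the Protocol; the investigators may prefer another value.

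No extra test is needed. The Day 1 blood count is already scheduled, and the stop rule already requires neutrophil counts. Sections 6.1 and 6.4 show no earlier screening count, so the existing white cell, platelet and haemoglobin criteria already need the Day 1 result before dosing. The cost is that an occasional woman with low neutrophils is not enrolled.
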